
 To explore the initial anti-tumor activity of GSK2857916 in subjects with relapsed/refractory MM in terms of time-to-event (TTE) endpoints (Part 2 MM) 	
 Time to progression (TTP), defined as: the time from first dose until the earliest date of PD per International Multiple Myeloma Working Group (IMWG), or death due to PD. Duration of response (DOR), defined as: the time from first documented evidence of PR or better; until the time when disease progression (PD) is documented per IMWG; or death due to PD occurs in subjects who achieve a response, i.e. confirmed PR or better. Time to response (TTR), defined as: the time between the date of first dose and the first documented evidence of response (PR or better), among subjects who achieve a response, i.e. confirmed PR or better. Time to best response (TTBR), defined as the time between the date of first dose and first documented evidence of the best response (PR or better), among subjects who achieve a response (i.e., confirmed PR or better). Progression-free survival (PFS), defined as: the time from first dose until the earliest date of disease progression (PD) per IMWG, or death due to any cause. Number of deaths.

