7.2.1. Multiple Myeloma

7.2.1.1. Endpoint / Variables

7.2.1.1.1. Overall Response Rate

Overall Response Rate (ORR), is defined as the percentage of responders (subjects with confirmed stringent complete response (sCR), complete response (CR), very good partial response (VGPR), and partial response (PR) as assessed according to 2011 International Myeloma Working Group (IMWG) criteria (Appendix 1 in the protocol)). Only the assessments from the start of treatment up to the earlier of disease progression or the start of new anti-cancer therapy will be considered. Only new systemic anti-cancer drugs taken are considered as anti-cancer therapy (radiotherapy and surgeries are not considered as systemic anti-cancer therapy for the purpose of this analysis). .

Subjects with only one assessment (therefore not confirmed), or assessments of Not Evaluable or missing response will be treated as non-responders; i.e. they will be included in the denominator when calculating the percentage.

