7.3.1.2.4. Time to Response

Time to Response (TTR) is defined as the time from first dose to the first documented evidence of confirmed PR or better, among subjects who achieve a response (i.e., confirmed PR or better).

TTR will be summarized using Kaplan-Meier method. If data permits, median TTR, first and third quartiles and 95% CI, will be estimated using the Brookmeyer-Crowley method [Brookmeyer, 1982]. A listing of TTR time will also be provided. Summary of TTR will be based on Part 2 MM population; listing of TTR will be based on All Treated MM population.

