BSTAGE	Stage at Screening	1 = I 2 = II 3 = III 4 =	When addc.PARAMCD = STAGESCR and AVALC = I, then BSTAGE = 1 When addc.PARAMCD = STAGESCR and AVALC = II, then BSTAGE = 2 When addc.PARAMCD = STAGESCR and AVALC = III, then BSTAGE = 3 When addc.PARAMCD = STAGESCR and AVALC = UNKNOWN or missing , then	addc

Column Header	Data Item	Codes	Derivation/Comments	Source data set
		UNKNOWN or missing	BSTAGE = 4 Fill on all rows	

For efficacy

General Description:

1. The dataset is sorted by SUBJID
2. Three significant figures for all values except those variables which are integers.
3. Only subjects with CANCER=0 will be included in this dataset as the data for the lymphoma patients will not be fully cleaned at the time of the database cut in 4Q2018.

Column Header	Data Item	Codes	Derivation/Comments	Source data set
C	Line number/exclusion identifier	Row Number	Set to line/row number	
STUDY	Study ID		1 = BMA117159	adsl
SUBJID	Subject identifier from source data		SUBJID = SUBJID	adsl
ID	NONMEM subject identifier		Sequential subject identifier across studies after data is sorted by SUBJID. Starting with P	derived
PFSCFLCD	PFS Censoring Flag Code	0 or 1	For PARAMCD=PFS_D, CNSR value is assigned to PFSCFLCD 0=Event 1=Censor	adtte
PFSD	PFS (Days)		For PARAMCD=PFS_D, AVAL value is assigned to PFSD When AVAL is missing for PFS_D, then PFSD = -99.	adtte
PFSM	PFS (Months)		For PARAMCD=PFS_M, AVAL value is assigned to PFSM When AVAL is missing for PFS_M, then PFSM = -99.	adtte
PFSY	PFS (Years)		For PARAMCD=PFS_D, (AVAL/365) value is assigned to PFSY When AVAL is missing for PFS_Y, then PFSY = -99.	derived
TTRCFLCD	TTR Censoring Flag Code	0 or 1	For PARAMCD=TTR_D, Assign 1 to TTRCFLCD. For subjects where TTR_D is missing, assign 0 to TTRCFLCD.	adtte
TTRD	TTR (Days)		For PARAMCD=TTR_D, AVAL value is assigned to TTRD. For subjects where TTR_D is missing, assign PFSD to TTRD.	adtte

Column Header	Data Item	Codes	Derivation/Comments	Source data set
TTRM	TTR (Months)		For PARAMCD=TTR_M, AVAL value is assigned to TTRM. For subjects where TTR_M is missing, assign PFSM to TTRM.	adtte
TTRY	TTR (Years)		For PARAMCD=TTR_D, (AVAL/365) value is assigned to TTRY. For subjects where TTR_D is missing, assign PFSY to TTRY.	derived
DORCFLCD	DOR Censoring Flag Code	0 or 1	For PARAMCD=DOR_D, CNSR value is assigned to DORCFLCD 0=Event 1=Censor Assign "." for missing.	adtte

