CUMAMTR	Cumulative dose to Response (mg)		
This is needed to derive Time-average AUC till response. For adtte.PARAMCD=TTR_D, • adex.PARAMCD=ALTDOSE, CUMAMTR= Cumulative of adex.AVAL starting from adtte.STARTDT and ending at adtte.ADT
 
• For response that occurred on dosing days, the dose on the response day was not included in the cumulative dose calculation. Here is the code for that: When adtte.ADT = adex.ASTDT at the last dose for that subject, then CUMAMTCT= Cumulative of adex.AVAL starting from adtte.STARTDT and ending at (adtte.ADT -1)
 
When TTRCFLCD=0 (i.e. subjects who did not respond), then CUMAMTR=TOTAMT
	adex, adtte
TAAUCR	Time-average AUC till response (AUC/day)		The area under the plasma ADC concentration–time curve (AUC) per day (AUC/day) will be derived for each patient using the available ADC dosing information, individual patient clearance values from the population pharmacokinetic model, and the time to the occurrence of the response	popPK output, adtte
AMT	Amount (in mg) of GSK2857916 given in first cycle		AMT = AVAL when PARAMCD=ALTDOSE and AVISIT= CYCLE 1 DAY 1	adex
IDOSE	GSK2857916 initial cycle dose (mg/kg)	>0	IDOSE=adex.TRT01A; strip off units	adex
CMAX	First dose Cmax of			PopPK

Column Header	Data Item	Codes	Derivation/Comments	Source data set
	ADC – model predicted EOI concentration in Cycle 1 (ng/mL)		Individual model predicted conc. at EOI.	output
MMAFCMAX	First dose C _{max} of MMAF – model predicted 24 HOURS POST-EOI in Cycle 1 (ng/mL)		Individual model predicted conc. at 24 HOURS POST-EOI in Cycle 1	PopPK output
CTAU	First dose C _{tau} of ADC– model predicted pre-dose concentration Cycle 2		Individual model predicted pre-dose conc.CYCLE 2.	PopPK output
AUC	First dose AUC(0-inf) of ADC (ug.day/mL)		First dose (mg)/Individual Clearance of ADC (L/Day)	popPK output
MMAFAUC	First dose AUC(0-inf) of MMAF (ug.day/mL)		First dose (mg)/Individual Clearance of MMAF (L/Day)	popPK output
TOTCYC	Total number of CYCLES		TOTCYC=AVAL, AVAL for adex.PARAM=Total Number of Cycles	adex
CANCER	Cancer type	0 or 1	0=Multiple Myeloma, 1=BCMA positive Lymphomas If TRT01AN = 12, then CANCER=1, else CANCER=0	adsl
ETHN	Subject ethnicity	Same coding as CRF/Stats	Fill in ETHN in all rows for each subject If missing, ETHN = -99	adsl
AGE	Age (years)		Use value as defined by Stats;	adsl
SEX	GENDER	0 or 1	Male = 1 Female = 0 • If sex is missing, GENDER = -99	adsl

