16.10.2.1.2. Clinical Response

Presence or absence of clinical response will be described using a conventional logistic regression model. Time to response will be explored using Kaplan Meier plots categorized by exposure measures.

PFS will be explored using Kaplan Meier plots categorized by exposure measures and occurrence of progression may also be described using a conventional logistic regression model.

Duration of response will be explored using Kaplan Meier plots categorized by exposure measures.

Best clinical response will be analyzed using an ordered logistic regression, with response categorized from 0 (progressive disease) to 6 (stringent complete response). Exposure will be treated as a categorical variable subdivided into quartiles and quintiles.

In the ordered logistic regression analyses, the use of categorical measures of exposure in lieu of continuous variables will allow for non-parametric descriptions of response functions.

Best clinical response as assessed by maximum reduction in M-protein or FLC will be analyzed by exposure (continuous and/or categorized by exposure measures).

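### The exploratory Kaplan-Meier plots of time to response by exposure treat progression and death as ordinary censoring, so they can overstate cumulative response and blur differences between exposure categories

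*SAP*

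**What the plan says.** In the efficacy table of SAP section 16.10.1, responders receive their time to response and TTRCFLCD=1. For the others the flag rule is "For subjects where TTR_D is missing, assign 0 to TTRCFLCD" and the time rule is "For subjects where TTR_D is missing, assign PFSD to TTRD". The months and years variables follow the same pattern. The meaning of the zero is settled in the cumulative-dose row: "When TTRCFLCD=0 (i.e. subjects who did not respond), then CUMAMTR=TOTAMT".

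The analysis is named in section 16.10.2.1.2: "Time to response will be explored using Kaplan Meier plots categorized by exposure measures". No competing-risk estimator or caveat accompanies it.

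Two definitions elsewhere matter. Section 2.2 defines PFS as "the time from first dose until the earliest date of disease progression (PD) per IMWG, or death due to any cause". For response, section 7.2.1.1.1 counts only assessments from the start of treatment "up to the earlier of disease progression or the start of new anti-cancer therapy will be considered".

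Two related analyses are set up differently. The main time-to-response analysis in section 7.3.1.2.4 is restricted to subjects with a confirmed response, and of it the SAP says: "Summary of TTR will be based on Part 2 MM population; listing of TTR will be based on All Treated MM population". In the exposure-response section itself: "Presence or absence of clinical response will be described using a conventional logistic regression model".

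**The concern.** Kaplan-Meier assumes that a censored subject would have gone on to have the event at the same rate as those still at risk. A non-responder who has progressed or died cannot respond under the SAP's own definition. Removing that subject as censored hands their share of the curve to those who remain, and one minus Kaplan-Meier is then no longer the probability of response.

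The distortion depends on how much progression occurs before later responses, and that may differ between exposure categories. A category with many early progressions is pushed up more than one with few. If lower exposure goes with earlier progression, the plotted curves move closer together than the true response proportions. At stake is the reading of the plan's only display of time to response by exposure.

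**Working it through.** The SAP states no figure for this analysis, so there is none to reproduce. The check compares the specified estimator with cumulative incidence, taking progression or death as a competing event.

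**Step 1: does the rule produce competing-risk censoring?** A non-responder has TTRCFLCD=0 and TTRD equal to the PFS time. PFSCFLCD in the same dataset is 0 for a PFS event and 1 for a PFS-censored subject. Non-responders are therefore of two kinds:
- PFSCFLCD=0: progression or death has occurred and response is no longer possible. Censoring here is the fault.
- PFSCFLCD=1: the subject left observation without a PFS event. Censoring here is ordinary, apart from new anti-cancer therapy (see the fix).

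**Step 2: an example that can be checked by hand** (invented data, 10 subjects per group).

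High exposure: responses at days 21, 42, 42 and 63; six progressions from day 105 on.
- 1−KM = 1 − (9/10)(7/9)(6/7) = 0.40
- Cumulative incidence = 4/10 = 0.40

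Low exposure: five progressions at day 21; responses at days 42 and 63; three progressions from day 105 on.
- 1−KM = 1 − (4/5)(3/4) = 0.40
- Cumulative incidence = 0.5 × 1/5 + 0.4 × 1/4 = 0.10 + 0.10 = 0.20

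True response is 40% against 20%, yet both Kaplan-Meier curves plateau at 40%. The high-exposure group shows no bias because every response precedes every progression.

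**Step 3: constant hazards** (assumed, not from the SAP; r = response and p = progression or death, per month; t = 12 months).

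1−KM = 1 − exp(−r·t)

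Cumulative incidence = r/(r+p) × [1 − exp(−(r+p)·t)]

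| r | p | True cumulative response | 1−KM |
|---|---|---|---|
| 0.15 | 0.15 | 0.5 × (1 − e^−3.6) = 49% | 1 − e^−1.8 = 83% |
| 0.05 | 0.20 | 0.2 × (1 − e^−3.0) = 19% | 1 − e^−0.6 = 45% |
| 0.15 | 0.05 | 0.75 × (1 − e^−2.4) = 68% | 1 − e^−1.8 = 83% |

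Rows 1 and 3 share a response hazard and differ in progression: 49% against 68% truly respond, while Kaplan-Meier shows 83% for both.

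**Step 4: simulation at the SAP's reference response rates.** Section 3.1.2.1.1 uses 20% and 40%, and the MM expansion cohort is up to 40 subjects. Assumed: responses spread evenly over the first six three-weekly visits, and every non-responder ending in progression or death. Mean 1−KM over 1000 runs, by assumed median PFS of non-responders:

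| True response | 1 month | 2 months | 3 months | 6 months |
|---|---|---|---|---|
| 20% | 0.58 | 0.35 | 0.29 | 0.24 |
| 40% | 0.82 | 0.61 | 0.53 | 0.46 |

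In these runs 1−KM exceeds cumulative incidence by a factor of 1.15 to 2.90. With a quarter of non-responders PFS-censored instead, the factor is 1.12 to 2.22.

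**The case against.** The best defence has four parts.

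- **The dataset rule is not itself at fault.** Aalen-Johansen needs exactly that time for a non-responder: the date of progression or death, or the PFS censoring date. This stands. The criticism belongs to the estimator in section 16.10.2.1.2, and TTRD should be left alone.
- **Kaplan-Meier has a legitimate reading.** With competing events censored, it describes the cause-specific response hazard, and two groups with equal response hazards should then look alike. This is correct, but the SAP does not name that target, and a reader will take the plateau as the proportion responding.
- **Inflation is not guaranteed, and its size is unknown.** Some non-responders are genuinely PFS-censored, and if responses come early the gap is modest, as the 6-month column shows. This also stands. A constant response hazard over 12 months produces a larger gap than early, clustered responses.
- **Other exposure analyses are sound.** The logistic regression of response, the ordered logistic regression of best response and the analysis of maximum M-protein or FLC reduction do not use this censoring. The main time-to-response summary contains responders only.

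A reader might infer that the plots could mislead the choice of dose. The SAP does not support that: nowhere does it say these plots support the dose, and section 12.1 describes exposure-response work that is reported separately. Nor do the documents support a claim that the curves will certainly plateau far above the observed response rate, since that depends on progression times they do not give.

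**Conclusion.** The point holds within limits. As specified, one minus Kaplan-Meier for time to response by exposure category is not the probability of response. It overstates cumulative response in any category where a progression or death precedes a later response, and it can reduce or remove visible differences between categories whose early progression differs.

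Under the assumptions shown, the overstatement ranges from small (0.46 against 0.40) to large (83% against 49%, or 0.58 against 0.20). All these sizes rest on assumed hazards or progression times. The direction rests only on the SAP's definitions.

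The consequence is confined to one set of exploratory plots. It is worth correcting because the plots could disagree with the logistic regression of response in the same section for no reason but the estimator.

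**What to change.** 1. Keep TTRD equal to the PFS time for non-responders.
2. In section 16.10.2.1.2, replace the Kaplan-Meier plot of time to response with Aalen-Johansen cumulative incidence of confirmed response by exposure category.
3. Define three outcomes from the existing flags: response (TTRCFLCD=1); competing event, progression or death before response (TTRCFLCD=0 and PFSCFLCD=0); censored at the PFS censoring date (TTRCFLCD=0 and PFSCFLCD=1). State this coding explicitly, because TTRCFLCD uses 1 for the event whereas PFSCFLCD uses 0.
4. Section 7.2.1.1.1 also rules out response after new anti-cancer therapy, while the PFS rules in section 7.3.1.2.1 censor such subjects. State whether starting new therapy before response is a further competing event or is censored.
5. If Kaplan-Meier is kept, label the plot as cause-specific and say that it does not show the probability of response.

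The cost is one changed plot and a few sentences. Steps 1 to 3 need no new data. Treating new therapy as a competing event would also need its start date, or the reason for PFS censoring, added to the dataset, since the efficacy specification lists neither.

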16.10.2. Pharmacokinetic / Pharmacodynamic Methodology

The primary goal of this analysis is to characterize the pharmacokinetic/pharmacodynamic relationships for GSK2857916 administered IV in subjects with multiple myeloma, data permitting. In these analyses, drug plasma concentration (or pharmacokinetic parameter) data and pharmacodynamic data will be subjected to logistic regression and time-to-event analyses, as appropriate, using suitable software. The influence of subject demographics and baseline characteristics, including

disease activity, in this population may be investigated. This analysis will be performed by CPMS and reported separately.

16.10.2.1. Exposure-Response Analyses

16.10.2.1.1. Corneal Events

Presence or absence of corneal events will be described using a conventional logistic regression model for both \geq Grade 1 and \geq Grade 2 toxicity. Time to first corneal event will be explored using Kaplan Meier plots categorized by exposure measures. Severity of corneal event will be analyzed using an ordered logistic regression model assuming Grades 0 (no toxicity), 1, 2 and 3, with exposure subdivided into quartiles and quintiles.

16.10.2.1.2. Clinical Response

Presence or absence of clinical response will be described using a conventional logistic regression model. Time to response will be explored using Kaplan Meier plots categorized by exposure measures.

PFS will be explored using Kaplan Meier plots categorized by exposure measures and occurrence of progression may also be described using a conventional logistic regression model.

Duration of response will be explored using Kaplan Meier plots categorized by exposure measures.

Best clinical response will be analyzed using an ordered logistic regression, with response categorized from 0 (progressive disease) to 6 (stringent complete response). Exposure will be treated as a categorical variable subdivided into quartiles and quintiles.

In the ordered logistic regression analyses, the use of categorical measures of exposure in lieu of continuous variables will allow for non-parametric descriptions of response functions.

Best clinical response as assessed by maximum reduction in M-protein or FLC will be analyzed by exposure (continuous and/or categorized by exposure measures).

16.11. Appendix 11: Abbreviations & Trade Marks**16.11.1. Abbreviations**

Abbreviation	Description
ADaM	Analysis Data Model
AE	Adverse Event
Ae(0-t)	Amount of drug excreted in urine from dosing to time t
AIC	Akaike's Information Criteria
A&R	Analysis and Reporting
AUC	Area under the concentration-time curve
CDISC	Clinical Data Interchange Standards Consortium
CI	Confidence Interval
CPMS	Clinical Pharmacology Modelling & Simulation
CR	Complete response
CS	Clinical Statistics
CSR	Clinical Study Report
CTR	Clinical Trial Register
CV _b / CV _w	Coefficient of Variation (Between) / Coefficient of Variation (Within)
DBF	Database Freeze
DBR	Database Release
CBR	Clinical benefit rate
CDISC	Clinical Data Interchange Standards Consortium
CI	Confidence interval
CK-MB	Creatine kinase MB-isoenzyme
CL	Clearance
C _{max}	Maximum observed plasma drug concentration
CPMS	Clinical Pharmacology Modeling and Simulation
CR	Complete response
CRM	Continual Reassessment Method
C _{trough}	Concentration observed prior to the next dose
Cys-mcMMAF	Cysteine-maleimidocaproyl monomethyl auristatin F
DLT	Dose limiting toxicity
DOB	Date of Birth
DOR	Duration of response
DP	Decimal Places
eDiary	Electronic Diary
ECOG	Eastern Cooperative Oncology Group
EOI	End of infusion
eCRF	Electronic Case Record Form
EMA	European Medicines Agency
FACTS	Fixed and adapted clinical trials simulator
FDA	Food and Drug Administration
FDAAA	Food and Drug Administration Clinical Results Disclosure Requirements
Fe(0-t)	Fraction of administered dose excreted in urine from dosing to time t
FLC	Free light chain

Abbreviation	Description
FTIH	First time in human
GSK	GlaxoSmithKline
IA	Interim Analysis
ICH	International Conference on Harmonization
IDMC	Independent Data Monitoring Committee
IDSL	Integrated Data Standards Library
IMMS	International Modules Management System
IP	Investigational Product
ITT	Intent-To-Treat
LDH	Lactate dehydrogenase
MMRM	Mixed Model Repeated Measures
MM	Multiple Myeloma
MMAF	Monomethyl auristatin F
MR	Minimal response
MTD	Maximum Tolerated Dose
NCI-CTCAE	National Cancer Institute – Common Terminology Criteria for Adverse Events
N-CRM	A modification of the Continual Reassessment Method (CRM) proposed by Neuenschwander et al.
NEI-VFQ-25	National Eye Institute Visual Functioning Questionnaire - 25
NONMEM	Nonlinear mixed effects modelling
ORR	Overall response rate
OS	Overall survival
OSDI	Ocular Surface Disease Index
PCI	Potential Clinical Importance
PD	Pharmacodynamics
PD	Progressive disease
PDMP	Protocol Deviation Management Plan
PET	Probability of early termination
PFS	Progression-free survival
PK	Pharmacokinetics
PP	Per Protocol
PR	Partial response
PopPK	Population PK
QC	Quality Control
QoL	Quality of life
QTcF	Fridericia's QT Interval Corrected for Heart Rate
QTcB	Bazett's QT Interval Corrected for Heart Rate
RAP	Reporting & Analysis Plan
RAMOS	Randomization & Medication Ordering System
REML	Restricted maximum likelihood
Ro	Observed accumulation ratio
RP2	Recommended Phase 2
SAC	Statistical Analysis Complete
SAE	Serious adverse event
sBCMA	Soluble B-cell maturation antigen

Abbreviation	Description
sCR	Stringent complete response
SD	Stable disease
SDSP	Study Data Standardization Plan
SDTM	Study Data Tabulation Model
SOI	Start of infusion
SPEP	Serum protein electrophoresis
SOP	Standard Operation Procedure
t _{1/2}	Terminal phase half-life
TA	Therapeutic Area
TFL	Tables, Figures & Listings
t _{last}	Time of last quantifiable concentration
t _{max}	Time to maximum drug concentration
TTBR	Time to best response
TTP	Time to progression
TTR	Time to response
ULN	Upper limit of normal
UPEP	Urine protein electrophoresis
VGPR	Very good partial response
V _{ss}	Volume of distribution at steady state

16.11.2. Trademarks

Trademarks of the GlaxoSmithKline Group of Companies
NONE

Trademarks not owned by the GlaxoSmithKline Group of Companies
FACTS
NONMEM
SAS
WinNonlin

16.12. Appendix 12: List of Data Displays

16.12.1. Data Display Numbering

The following numbering will be applied for RAP generated displays:

Section	Tables	Figures
Study Population	1.0010 to 1.xxxx	11.0010 to 11.xxxx
Efficacy	2.0010 to 2.xxxx	12.0010 to 12.xxxx
Safety	3.0010 to 3.xxxx	13.0010 to 13.xxxx
Pharmacokinetic	4.0010 to 4.xxxx	14.0010 to 14.xxxx
Population Pharmacokinetic (PopPK)	5.0010 to 5.xxxx	15.0010 to 15.xxxx
Pharmacodynamic and / or Biomarker	6.0010 to 6.xxxx	16.0010 to 16.xxxx
Pharmacokinetic / Pharmacodynamic	7.0010 to 7.xxxx	17.0010 to 17.xxxx
Section	Listings	
ICH Listings	1.0010 to 1.xxxx	
Other Listings	30.0010 to 30.xxxx	

